**Death**

See "mortality"

**Device deficiency**

Inadequacy of a medical device related to its identity, quality, durability, reliability, safety or performance.

NOTE: Device deficiencies include malfunction, use error, and inadequate labeling. They may or may not affect device performance or lead to an adverse event.

**Device malfunction**

Failure of an investigational medical device to perform in accordance with its intended purpose when used in accordance with the Instructions for Use or protocol.

NOTE: A device malfunction occurs when the device is used in compliance with the Instructions for Use but does not perform as described in the Instructions for Use.

**Device misuse**

Any use of the investigational device by an investigator that is contradictory to the application described in the Instructions for Use will be categorized as device misuse. This is a form of Use Error.

**Device success**

Successful implantation of the CLAAS device in the LAA with acceptable position and seal (peri-device residual leak  $\leq 5$  mm in width [evaluated post-procedure])

**Embolic events**

A composite of ischemic stroke and systemic thromboembolism

**HAS-BLED Score**

A scoring system to assess the risk of major bleeding in patients with atrial fibrillation receiving oral anticoagulation (OAC) therapy. Patients are assigned a score from 0 to 9 by adding the points for each applicable clinical characteristic below to obtain a total score:

Clinical Characteristic	Score
Hypertension	1
Abnormal renal and liver function (1 point each)	1 or 2
Stroke	1
Bleeding history or predisposition	1
Labile INRs in patients taking warfarin	1

Elderly (> 65 years)	1
Drugs (concomitant antiplatelet agents or NSAIDs) or alcohol abuse (1 point each)	1 or 2

Implanted Patient (IP) Population	All subjects who leave the catheterization laboratory after the index procedure with an implanted CLAAS device
Intention to Treat (ITT) Population	All subjects enrolled in the study (the point of enrollment is introduction of the CLAAS delivery system into the patient's body), regardless of the treatment actually received.
Ischemic stroke	
NeuroARC-defined Type 1.a or 1.a.H overt CNS injury:
 
Type 1.a Ischemic stroke
 
Sudden onset of neurological signs or symptoms fitting a focal or multifocal vascular territory within the brain, spinal cord, or retina, that:
 
 
1) Persist for <math>\geq 24</math> h or until death, with pathology or neuroimaging evidence that demonstrates either: 
 
a) CNS infarction in the corresponding vascular territory (with or without hemorrhage); or
 
b) Absence of other apparent causes (including hemorrhage), even if no evidence of acute ischemia in the corresponding vascular territory is detected
 
 
or
 
 
2) Symptoms lasting <math><24</math> h, with pathology or neuroimaging confirmation of CNS infarction in the corresponding vascular territory. Note: When CNS infarction location does not match the transient symptoms, the event would be classified as covert CNS infarction (Type 2a) and a TIA (Type 3a), but not as an ischemic stroke.
 
 
Signs and symptoms consistent with stroke typically include an acute onset of 1 of the following: focal weakness and/or numbness; impaired language production or comprehension; homonymous hemianopia or quadrantanopsia; diplopia; altitudinal monocular blindness; hemispatial neglect; dysarthria; vertigo; or ataxia.
 
Subtype 1.a.H Ischemic stroke with hemorrhagic conversion
 
Ischemic stroke includes hemorrhagic conversions. These should be subclassified as Class A or B when ischemic stroke is the primary mechanism and pathology or neuroimaging confirms a hemorrhagic conversion.

	
Class A (Petechial hemorrhage): Petechiae or confluent petechiae within the infarction or its margins, but without a space-occupying effect
 
Class B (Confluent hemorrhage): Confluent hemorrhage or hematoma originating from within the infarcted area with space-occupying effect

Major endovascular intervention	Major endovascular intervention includes pseudoaneurysm repair, AV fistula repair, and other major endovascular repair. The following interventions are not considered major endovascular interventions: percutaneous catheter drainage of pericardial effusions, percutaneous retrieval of an embolized device, thrombin injection to treat femoral pseudoaneurysm, and nonsurgical treatments of access site complications.
Major procedure-related complications	A composite of cardiac perforation, pericardial effusion with tamponade, ischemic stroke, device embolization, and major vascular complications, adjudicated by the independent Clinical Events Committee as related to the study device or procedure
Major safety events	A composite of all-cause mortality, overt CNS injury, and major bleeding
Mortality	
Classified as cardiovascular (defined as cardiac or vascular) or noncardiovascular according to the following ARC definitions. All deaths are considered cardiac unless an unequivocal noncardiac cause can be established. Specifically, any unexpected death even in patients with coexisting potentially fatal noncardiac disease (e.g., cancer, infection) should be classified as cardiac.
 
 
• Cardiac death: Any death due to proximate cardiac cause (e.g., MI, low-output failure, fatal arrhythmia), unwitnessed death and death of unknown cause, and all procedure-related deaths, including those related to concomitant treatment, will be classified as cardiac death.
 
• Vascular death: Death caused by noncoronary vascular causes, such as cerebrovascular disease, pulmonary embolism, ruptured aortic aneurysm, dissecting aneurysm, or other vascular diseases.
 
 
Noncardiovascular death: Any death not covered by the above definitions, such as death caused by infection, malignancy, sepsis, pulmonary causes, accident, suicide, or trauma.

Myocardial infarction	
Defined according to VARC-2 as:
 
Peri-procedural MI (<math>\leq 72</math> h after the index procedure):
 
 
• New ischemic symptoms (e.g. chest pain or shortness of breath), or new ischemic signs (e.g. ventricular arrhythmias, new or worsening heart failure, new ST-segment changes, hemodynamic instability, new pathological Q waves in at least two contiguous leads, imaging
 

evidence of new loss of viable myocardium or new wall motion abnormality) AND

- Elevated cardiac biomarkers (preferably CK-MB) within 72 h after the index procedure consisting of at least one sample post-procedure with a peak value exceeding 15x upper reference limit for troponin or 5x for CK-MB. If cardiac biomarkers are increased at baseline ( $>99^{\text{th}}$  percentile), a further increase of at least 50% post-procedure is required AND the peak value must exceed the previously stated limit.

Spontaneous MI ( $>72$  h after the index procedure). Any one of the following criteria:

- Detection of rise and/or fall of cardiac biomarkers (preferably troponin) with at least one value above the 99th percentile URL, together with evidence of myocardial ischemia with at least one of the following:
  - Symptoms of ischemia
  - ECG changes indicative of new ischemia [new ST-T changes or new left bundle branch block (LBBB)]
  - New pathological Q waves in at least two contiguous leads
  - Imaging evidence of new loss of viable myocardium or new wall motion abnormality
- Sudden, unexpected cardiac death, involving cardiac arrest, often with symptoms suggestive of myocardial ischemia, and accompanied by presumably new ST elevation, or new LBBB, and/or evidence of fresh thrombus by coronary angiography and/or at autopsy, but death occurring before blood samples could be obtained, or at a time before the appearance of cardiac biomarkers in the blood.
- Pathological findings of an acute myocardial infarction.

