### 5.3 Endpoints

#### 5.3.1 Primary Safety Endpoint

The primary safety endpoint is **freedom from major adverse events**, evaluated at hospital discharge or at 7 days post-procedure (whichever occurs later), and defined as absence of the composite of:

- All-cause mortality
- Ischemic stroke
- Systemic thromboembolism

- Device- or procedure-related adverse events requiring open cardiac surgery or major endovascular intervention\*

\*NOTE: Major endovascular intervention includes pseudoaneurysm repair, arteriovenous fistula repair, and other major endovascular repair. Non-major interventions that are excluded from this endpoint include percutaneous catheter drainage of pericardial effusions, percutaneous retrieval of an embolized device, thrombin injection to treat femoral pseudoaneurysm, and nonsurgical treatments of access site complications.

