#### 5.3.3.3 Secondary Effectiveness Endpoint

5.3.3.3.1 **Emolic events**, defined as the composite of ischemic stroke and systemic embolism

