	
survival status, QVSFS, concomitant medication documentation, and reporting of any adverse events that may have occurred since the pre-discharge assessment.
 
The Questionnaire for Verifying Stroke-Free Status (QVSFS) and NIHSS must be completed at baseline and during each clinic visit to screen for interceding signs and symptoms of stroke or TIA. The modified Rankin Scale (mRS) must also be completed at baseline to establish the pre-stroke baseline value. For telephone contacts, stroke screening will consist of the QVSFS only. If a neurologic event is suspected at any time point, a formal neurologic examination and evaluation (to include the mRS) must be performed by a neurologist.
 
 Female subjects of childbearing potential must have a pregnancy test (by site standard method) within 7 days prior to the index procedure to confirm study eligibility criteria.
 
 Laboratory testing should be performed per site standard practice and should include CBC and serum creatinine.
 
 A 12-lead ECG should be performed at baseline and repeated with any signs or symptoms of myocardial ischemia.
 
 Patients with a history of stroke are required to have a baseline MRI (or CT, if MRI is contraindicated) performed within 90 days prior to the scheduled index procedure. Brain imaging need not be repeated if an MRI or CT performed within 90 days pre-procedure as part of the standard of care is available. Patients with history of significant brain trauma or intra-cranial surgery should have a post procedure/event CT or MRI available for review.
 
 An initial evaluation of echocardiographic eligibility based on review of the pre-procedure TTE and/or TEE (or cardiac CT, if that modality is the site standard of care for pre-procedure anatomic assessment) should be performed prior to the index procedure.
 
 TEE (or CT) performed within 90 days prior to consent will be accepted, otherwise TEE must be conducted after consent.
 
TTE performed within 6 months prior to consent will be accepted, otherwise TTE must be conducted after consent.
 
TEE performed after implant delivered, prior to tether release.
 
At time of index procedure, ICE performed to confirm eligibility criteria prior to enrollment.

--	---

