## 7.5 Pre-discharge Follow-up

Post-procedure assessment must occur during the index procedure hospitalization prior to hospital discharge, and must include:

- Physical examination
- TTE
- Stroke assessment, to include:
  - Questionnaire for Verifying Stroke-Free Status (QVSFS)
  - NIH Stroke Scale (NIHSS); the NIHSS must be performed by a neurologist or NIHSS-certified research staff
  - Patients in whom a neurologic event is suspected on the basis of the QVSFS, NIHSS, or other signs or symptoms will require a neurologic examination and evaluation performed by a neurologist or clinical designee (e.g., neurology fellow). In patients with confirmed stroke, mRS must be documented, and repeated 90 ± 14 days post-event to assess disability.
- Current concomitant medications documentation. If DAPT has been interrupted or terminated the stop date (and resumption date, if applicable) and the reason for interruption/termination should be recorded.

Prior to hospital discharge, research staff should review the follow-up requirements with the subject to ensure compliance with the subsequent follow-up assessment:

- For subjects discharged from the index procedure hospitalization on or before day 6 post-procedure, telephone numbers should be obtained from the subject to ensure the ability to reach him or her for the required 7 + 2-day telephone contact. These phone numbers should

include all home numbers, work numbers and primary physician numbers. A phone number of a relative or friend should also be requested.

- For subjects discharged from the index procedure hospitalization on day 7 or later post-procedure, telephone numbers should be obtained from the subject to ensure that the subject returns to the clinic for the 45-day follow-up assessment.

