**CHA2DS2-VASc Score**

A clinical risk stratification scheme for predicting stroke and thromboembolism in patients with nonvalvular AF, updated from the earlier CHADS2 score. Patients are assigned a score from 0 to 9 by adding the points for each applicable risk factor below to obtain a total score:

Risk Factors	Score
Congestive Heart Failure	1
Hypertension	1
Age $\geq 75$ years	2
Diabetes mellitus	1
Stroke/TIA/thromboembolic event in the past	2
Vascular disease (prior MI, PAD, or aortic plaque)	1
Age 65 to 74 years	1
Sex category (female gender)	1

Closure success	Device success (see definition) followed by successful LAA closure (complete closure or peri-device residual leak $\leq 5$ mm in width on TEE at 45 days post-procedure). NOTE: The primary protocol definition of closure success is at the primary performance endpoint evaluation time point of 45 days; closure success at 6 and 12 months will also be evaluated.
CNS hemorrhage	NeuroARC defined  as any brain, spinal cord, or retinal hemorrhage on the basis of imaging or pathology, not caused by trauma (includes symptomatic intracerebral hemorrhage [Type 1.b], symptomatic subarachnoid hemorrhage [Type 1.c], and covert CNS hemorrhage [Type 2.b])
CNS infarction	NeuroARC defined  as any brain, spinal cord, or retinal infarction on the basis of imaging, pathology, or clinical symptoms persisting for $\geq 24$ h (includes ischemic stroke [Type 1.a], ischemic stroke with hemorrhagic conversion [Type 1.a.H], stroke not otherwise specified [Type 1.d], symptomatic hypoxic-ischemic injury [Type 1.e], covert CNS infarction [Type 2.a], and covert CNS infarction with hemorrhagic conversion [Type 2.a.H])
Composite efficacy	Freedom from the composite of all-cause mortality, all stroke, TIA, and systemic thromboembolism

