**Type 1.d Stroke, not otherwise specified**

An episode of acute focal neurological signs or symptoms and/or headache presumed to be caused by CNS ischemia or CNS hemorrhage, persisting ≥24 h or until death, but without sufficient evidence to be classified as either (i.e., no neuroimaging performed)

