Transient ischemic attack (TIA)	NeuroARC defined  as transient focal neurological signs or symptoms (lasting <24 h) presumed to be due to focal brain, spinal cord, or retinal ischemia, but without evidence of acute infarction by neuroimaging or pathology (or in the absence of imaging).
Unanticipated Adverse	An unanticipated adverse device effect is any serious adverse effect on the health or safety or any life-threatening problem or death caused by, or

**Device Effect (UADE)** associated with, a device, if that effect, problem, or death was not previously identified in nature, severity or degree of incidence in the investigational plan or application (including a supplementary plan or application), or any other unanticipated serious problem associated with a device that relates to the rights, safety or welfare of subjects.

NOTE: An anticipated serious adverse device effect (ASADE) is a serious adverse device effect which by its nature, incidence, severity, or outcome has been identified in the investigational plan or application (including a supplementary plan or application).

**Use Error** Act or omission of an act that results in a different medical device response than intended by the manufacturer or expected by the user.

NOTE 1: Use error includes slips, lapses and mistakes.

NOTE 2: An unexpected physiological response of the patient does not itself constitute a use error.

**Vascular complications** VARC-2 defined as:

Major Vascular Complications:

- Any aortic dissection, aortic rupture, annulus rupture, left ventricle perforation, or new apical aneurysm/pseudo-aneurysm OR
- Access site or access-related vascular injury (dissection, stenosis, perforation, rupture, arterio-venous fistula, pseudoaneurysm, hematoma, irreversible nerve injury, compartment syndrome, percutaneous closure device failure) **leading to** death, life-threatening or major bleeding, visceral ischemia or neurological impairment OR
- Distal embolization (non-cerebral) from a vascular source requiring surgery or resulting in amputation or irreversible end-organ damage OR
- The use of unplanned endovascular or surgical intervention **associated** with death, major bleeding, visceral ischemia or neurological impairment OR
- Any new ipsilateral lower extremity ischemia documented by patient symptoms, physical exam, and/or decreased or absent blood flow on lower extremity angiogram OR
- Surgery for access site-related nerve injury OR

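### A non-fatal clinical stroke that is never scanned (NeuroARC Type 1.d) leaves the subject event-free on the primary safety endpoint but counts in a secondary one

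*Combined protocol and SAP*

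**What the plan says.** References are to protocol Version B; the definitions read the same in Version A.

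- **Endpoint.** The primary safety endpoint (5.3.1) is "evaluated at hospital discharge or at 7 days post-procedure (whichever occurs later"). Its components are death from any cause, ischemic stroke, systemic thromboembolism, and device- or procedure-related events needing open cardiac surgery or major endovascular intervention.
- **What counts as ischemic stroke.** Appendix A restricts it to "Type 1.a or 1.a.H overt CNS injury". A deficit of 24 h or more needs imaging or pathology that either shows infarction (limb 1a) or leaves no other apparent cause, even with no ischemia seen (limb 1b). A deficit under 24 h needs confirmed infarction.
- **What happens without a scan.** A longer clinical stroke becomes Type 1.d, "but without sufficient evidence to be classified as either (i.e., no neuroimaging performed"). A short deficit becomes a TIA, "but without evidence of acute infarction by neuroimaging or pathology (or in the absence of imaging").
- **Work-up of a suspected event.** Table 3, footnote 3, says that "a formal neurologic examination and evaluation (to include the mRS) must be performed by a neurologist". Sections 7.5 to 7.9 and Appendices C to E likewise ask for an examination and evaluation, with scales. None names CT or MRI. Section 7.5 adds: "In patients with confirmed stroke, mRS must be documented, and repeated 90 ± 14 days post-event to assess disability". It does not say how a stroke is confirmed.
- **Other endpoints.** Embolic events are "defined as the composite of ischemic stroke and systemic embolism", and major procedure-related complications also name ischemic stroke. Major safety events use overt CNS injury, which includes Type 1.d.

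**The concern.** Whether a non-fatal stroke enters the primary safety result depends on whether a scan was obtained, and the plan does not require one when a stroke is suspected. Two subjects with the same lasting deficit, one scanned and one not, could be classified differently. The primary safety endpoint could then show no event while the secondary major safety events show a stroke in the same subject.

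The results are meant to inform the design of a pivotal trial (4.3), and with 20 subjects a single classification is visible in the headline figure. Section 10 is the only analysis plan in the documents. It makes no adjustment for missing data (10.3.3) and plans no analysis that would show the effect of this rule.

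**Working it through.** **1. Where each presentation lands (surviving subject, no other component of the composite)**

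| Presentation | Appendix A class | Primary safety event? | Major safety event? |
|---|---|---|---|
| 24 h or more, scan shows infarct | 1.a or 1.a.H | Yes | Yes |
| 24 h or more, scan shows no ischemia, other causes excluded | 1.a, limb 1(b) | Yes | Yes |
| 24 h or more, no scan or pathology | 1.d | **No** | **Yes** |
| Under 24 h, infarct confirmed | 1.a or 1.a.H | Yes | Yes |
| Under 24 h, no scan | TIA | No | No |

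The third row is the gap.

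**2. Does the schedule close it?** The Brain Imaging row of Table 3 carries a mark at pre-discharge as well as at screening. Footnote 7 covers baseline imaging in patients with prior stroke, and availability of a scan where there is a history of brain trauma or intracranial surgery. The required list in 7.5 has no brain imaging. The mark is therefore unexplained. If it is genuine it could catch in-hospital events, but not events between discharge and day 7, which are still inside the endpoint window.

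**3. Size of one case.** The plan states no precision or power figure to reproduce: 10.1 gives 20 subjects without inputs, and 10.3.1 rules out hypothesis testing. Exact (Clopper-Pearson) 95% limits with n = 20:

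- No counted event: 20/20 = 100%. Lower limit = 0.025^(1/20) = 0.832, giving 83.2% to 100%.
- One counted event: 19/20 = 95.0%. Upper limit = 0.975^(1/20) = 0.999. Lower limit = 1 − p, where (1 − p)^20 + 20p(1 − p)^19 = 0.025, so p = 0.249 and the limit is 0.751. This gives 75.1% to 99.9%.

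Each reclassified subject moves the estimate by 1/20 = 5 percentage points.

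**4. How likely is one case?** The documents give neither a stroke rate for the window nor the share left unscanned. As an assumption only, take a rate r of 0.5% to 5% and an unscanned share f of 10% to 50%. P(at least one in 20) = 1 − (1 − r·f)^20:

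- r = 0.5%, f = 10%: 1 − 0.9995^20 = 1.0%
- r = 2%, f = 25%: 1 − 0.995^20 = 9.5%
- r = 5%, f = 50%: 1 − 0.975^20 = 39.7%

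The range is wide because nothing in the documents narrows it.

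**The case against.** The strongest reply is that the plan uses a recognised classification, that the event is visible elsewhere, and that the study is small and descriptive. Much of this stands. Type 1.d is counted in major safety events in hospital and at 45 days, 6 and 12 months. A fatal stroke counts through all-cause mortality. Strokes and TIAs also appear in the adverse event tables and listings (10.3.4). Keeping TIA out of a stroke endpoint is a defensible choice. A shift of 5 points is what any single event does with 20 subjects. None of this changes the primary figure, which can still omit a clinical stroke because no scan was done.

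A reader might infer more than the documents support:

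- *That only strokes proven by a positive scan count.* Limb 1(b) accepts a persistent deficit with a scan showing no ischemia. The scan must exist; it need not be positive.
- *That the protocol contains no brain imaging after the procedure.* The pre-discharge mark in Table 3 prevents so flat a statement.
- *That most subjects are screened by telephone at day 7, where a scan is least likely.* No length of stay is given, in-hospital or clinic assessment is allowed (7.6), and a positive questionnaire answer triggers a formal neurologic evaluation.
- *That Appendix A contradicts itself because its CNS infarction entry lists* "stroke not otherwise specified [Type 1.d"]. That entry is a broad category which no endpoint uses. A broad category beside a narrower endpoint term is not a contradiction.
- *That every Type 1.d event is a missed ischemic stroke.* Type 1.d covers strokes presumed to be ischemic or hemorrhagic, and non-fatal hemorrhagic stroke is not in the primary composite. Excluding cases with hemorrhage shown on imaging would do almost nothing, since Type 1.d lacks that evidence by definition.

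**Conclusion.** The point holds for Type 1.d. As written, the primary safety endpoint can record a surviving subject with an unscanned clinical stroke as event-free while a secondary endpoint records an event. If this happened once in 20 subjects, the result would read 100% (83.2 to 100) instead of 95.0% (75.1 to 99.9). That comparison assumes the case occurs, is the only event, and all 20 subjects are evaluable. The documents give no basis for how probable it is.

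This is a should-fix. The definition follows a published scheme, the study tests no hypothesis, and the event is not lost from the report. But the headline safety figure should not depend on whether a scan happened to be done, and the remedy is cheap. The Clinical Events Committee's stated role (9.3) is to judge relatedness to device and procedure, so it does not resolve the matter.

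**What to change.** 1. In 5.3.1 and Appendix A, count Type 1.d as an event in the primary safety composite, which is the conservative choice for safety. At minimum, pre-specify in section 10.3.3 that the primary safety endpoint is reported both with and without Type 1.d.
2. For major procedure-related complications (5.3.3.1.1) and embolic events (5.3.3.3.1), report Type 1.d as a supplementary line. Do not relabel it ischemic or embolic.
3. List TIAs classified without imaging separately.
4. Reconcile the pre-discharge Brain Imaging mark in Table 3 with footnote 7 and section 7.5.

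The counting rule should be fixed before results are examined, because a rule chosen after an event is known would not be credible.

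**Cost.** Items 1 to 3 change wording and add table lines, with no added procedure. Item 4 is a correction of text. The safety figure may be slightly less favourable, and counting Type 1.d may bring in an unscanned hemorrhage.
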